#### **14.2.34 Programming rules**

The following should be used for programming of efficacy results:

#### **14.2.35 Calculation of 'time to event' variables**

Time to event = end date - start date + 1 (in days)

When no post-baseline tumor assessments are available, the date of randomization/start of treatment will be used as end date (duration = 1 day) when time is to be censored at last tumor assessment, i.e. time to event variables can never be negative.

#### **14.2.36 Incomplete assessment dates**

All investigation dates (e.g. X-ray, CT scan) must be completed with day, month and year.

If one or more investigation dates are incomplete but other investigation dates are available, this/these incomplete date(s) are not considered for calculation of the assessment date (and assessment date is calculated as outlined in [Section 14.2.26](#)). If all measurement dates have no day recorded, the 1st of the month is used.

If the month is not completed, for any of the investigations, the respective assessment will be considered to be at the date which is exactly between previous and following assessment. If a previous and following assessment is not available, this assessment will not be used for any calculation.

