#### **4.1.4 Efficacy follow-up**

Patients who discontinue treatment for reasons other than disease progression or withdrawal of consent for efficacy follow-up, will continue to be followed every 8 weeks for efficacy (i.e., tumor assessments and patient reported outcomes) during the first 18 months, then every 12 weeks until 36 months and thereafter as clinically indicated until disease progression, death, withdrawal of consent, loss to follow-up, subject/guardian decision. All scans will be acquired and analyzed for primary endpoint locally and will be sent to the CRO designated by Novartis for central imaging interpretation. If a patient starts a new anti-neoplastic treatment without withdrawing consent, the patient will continue to be followed for efficacy according to above specified protocol schedule until disease progression, death, withdrawal of consent, loss to follow-up, or subject/guardian decision. For further details please refer to [Table 7-1a](#) and [Table 7-1b](#) and [Section 7.1.6](#).

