#### **14.2.37 Incomplete dates for last known date patient alive or death**

[figure not shown]
All dates must be completed with day, month and year. If the day is missing, the 15th of the month will be used for incomplete death dates or dates of last contact.

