2.5 Implementation of RECIST

Response and progression evaluation will be performed according to the Novartis RECIST guideline (as described in detail in Appendix 2 of the Clinical Study Protocol), which is based on the RECIST 1.1 guidelines ([Eisenhauer et al 2009](#)). The text below gives instructions and rules to provide details needed for programming.

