If OS is statistically significant, a stratified multivariate Cox proportional hazard model adjusting for covariates will be fitted, including the treatment arm and the following key potential prognostic factors as covariates: age (≥ 65 vs < 65), prior chemo therapy in (neo)adjuvant setting (yes vs no), ECOG performance status (0 vs. 1), and bone only lesion at baseline (yes or no). In addition, stratified multivariate Cox models will be fitted including treatment arm and each of these factors individually, including treatment by factor interaction, to explore the relationship between each factor and treatment.

[REDACTED]

The pattern of censored data will be examined between the treatment arms: reasons for censoring ('Alive' or 'Lost to follow-up') and death cause will be summarized by treatment arm. In addition, survival status, reason for censoring and death cause will be listed. Patients not known to have died will be censored as 'Lost to follow-up' if the time between their last contact date and the analysis cut-off date is longer than the protocol specified interval between the survival follow-up assessments plus 2 weeks, i.e., 14 weeks (98 days) for this study.

Handling missing month/day in date of death

For rare cases when either day is missing or both month and day are missing for the date of death, the following imputation rules will be implemented:

- If only day is missing, then date of death is imputed as max [(1 mmm-yyyy), min(last contact date +1, cutoff date)].
- If both day and month are missing, then date of death is imputed as max [(1 Jan-yyyy), min (last contact date +1, cutoff date)].

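### Protocol 14.2.36 drops a progression assessment that has no usable month and no later scan, so a recorded PFS event becomes censoring

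*Protocol*

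**What the plan says.** Protocol 14.2.36 requires a full date for every investigation and then sets rules for gaps. The first, on how an assessment is dated, reads "If one or more investigation dates are incomplete but other investigation dates are available, this/these incomplete date(s) are not considered for calculation". The second covers an assessment whose dates all lack the day: the first of the month is used. The third covers a missing month: the assessment "will be considered to be at the date which is exactly between previous and following assessment". The discard sentence follows: "If a previous and following assessment is not available, this assessment will not be used for any calculation".

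Under Protocol 4.1.4, tumour assessments continue "until disease progression, death, withdrawal of consent, loss to follow-up, subject/guardian decision". Section 7.1.6 and Table 7-2 stop at the same point. The Table 7-2 footnote does not normally require an end-of-treatment scan once the previous one has shown progression.

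The SAP for the primary PFS analysis says in 2.5 that "Response and progression evaluation will be performed according to the Novartis RECIST guideline", as set out in Appendix 2. Its own date imputations (3.8.1.5 and 3.8.2.1) concern dates of death. Section 2.5.2 does not count progression given as a reason for discontinuation unless the RECIST pages support it. Sections 2.5.5 and 3.8.1.1 censor at the last adequate assessment when there is no event, or when the event comes more than D2 after that assessment.

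**The concern.** A midpoint needs an assessment on each side. The assessment that carries progression is usually the last one, so the month rule fails for the very record that defines the primary endpoint. A stable-disease scan with the same gap would usually be kept, because another scan follows it. The data are therefore discarded selectively, at the moment of failure.

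The patient is then censored at a time when the investigator's record already shows progression by the next assessment. Such censoring is informative: it removes failures from the risk set just before they happen and tends to raise the Kaplan-Meier PFS curve of whichever arm it occurs in.

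The wording adds a second problem. The month sentence can be read as triggered by one undated investigation, whereas the first sentence ignores such a date when others are available. Two programmers could derive different PFS outcomes from one record.

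**Working it through.** **1. The plan's own figure.** Inputs from Protocol 10.8: hazard ratio 0.67, one-sided 2.5%, 95% power, 2:1 allocation. By Schoenfeld's formula, events = (1.960 + 1.645)² / [(2/3)(1/3)(ln 0.67)²] = 12.995 / 0.03564 = 364.6, rounded up to 365, against 364 stated. Power with 364 events = Φ(√(364 × 0.03564) − 1.960) = Φ(1.642) = 94.97%, against 95% stated. The design reproduces.

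**2. Tracing one record.** Last adequate scan at week 40 (C11D1 in SAP Table 2-3); progression at week 48; no investigation at week 48 has a month; no later scan.

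- There is no following assessment, so no midpoint can be formed and the week 48 assessment is unused.
- PFS is censored at week 40.
- D2 here is 2 × 8 + 2 = 18 weeks, so a death up to week 40 + 18 = 58 still counts, dated at death. A death at week 55 would be an event 55 − 48 = 7 weeks after the recorded progression.
- A death at week 60 lies beyond week 58 and is also censored at week 40.

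D2 is 22 weeks when the last adequate scan matches C17D1 and 26 weeks from C19D1 on. Had the week 48 scan lacked only its day, the progression would have been kept and dated to the first of the month.

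**3. Size.** The documents give no rate of missing months, so these rates are assumptions. Lost events = rate × 364; power uses the formula in step 1.

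| Assumed share of events lost | Events lost | Power |
|---|---|---|
| 0.1% | 0.4 | 94.95% |
| 0.5% | 1.8 | 94.9% |
| 1% | 3.6 | 94.8% |
| 2% | 7.3 | 94.6% |
| 5% | 18.2 | 94.0% |

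These are losses against a fixed 364. If the trigger counts events after the rule is applied, the cost is a later cut-off instead of lost power.

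**4. The two sentences side by side.** Take a progression visit with a fully dated CT and one bone film lacking its month. Under "If one or more investigation dates are incomplete but other investigation dates are available", the film's date is ignored and progression takes the CT date. If the month sentence is read as needing only one undated investigation, the whole assessment goes to the midpoint rule and, with no later scan, is dropped. The first reading is the more natural, but the text does not settle it.

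**The case against.** The strongest reply is that this hardly ever happens. Full dates are mandatory (14.2.36), the eCRF is validated automatically (Protocol 9.3), missing values are queried (9.4), and scans went promptly to the imaging CRO for quality control (7.2.1.1) until central review ended. Every investigation at a progression visit would have to lack its month after all that. This stands, and it keeps the expected effect small.

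Other safeguards help only in part. The planned sensitivity analysis that takes events whenever they occur would count a later death, but it would not restore the progression. Central review is supportive and covers about 40% of patients. A repeat scan, for example of an equivocal new lesion, would supply a following assessment. Protocol 14.2.29 calls these rules guidance, but 14.2.34 directs their use in programming efficacy results and SAP 2.5 adopts the appendix. No further formal PFS analysis is planned, and the SAP for the final CSR contains none; Protocol 10.4.4 still allows descriptive ones.

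Four stronger readings are tempting, and the documents do not support them:

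- *One undated film deletes the progression.* The first sentence of 14.2.36 most naturally prevents this.
- *Every affected patient is censored.* A death within D2 still counts.
- *The hazard ratio is biased towards ribociclib.* Treatment was blinded through the primary analysis, and nothing suggests that missing months depend on arm.
- *Death dates share the fault.* Under Protocol 14.2.37 the 15th "of the month will be used for incomplete death dates or dates of last contact", which differs from SAP 3.8.2.1 ("If only day is missing, then date of death is imputed as max" of the first of that month and a second date). That second date is the earlier of last contact + 1 day and the cut-off. The SAP rule is specific, already bounded, and governs the analysis.

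**Conclusion.** The point holds within these limits. When no investigation at a progression assessment has a usable month and no assessment follows, Protocol 14.2.36, applied through SAP 2.5, discards a recorded progression and censors PFS at the last adequate scan unless death follows within D2. Nothing in the SAP overrides this.

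The expected numerical effect is small: under the assumed range of 0.1% to 5%, power stays at 94.0% or above. No direction of bias in the hazard ratio is shown. The conclusion rests on reading the discard sentence as applying when either neighbour is absent; that is the only workable reading, since a midpoint needs both. The rule should be corrected because it gives the wrong result whenever it applies to a last progression scan, and correcting it costs almost nothing.

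**What to change.** In Protocol 14.2.36 and the SAP governing PFS, state that:

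1. If any investigation at the assessment is fully dated, those dates are used. The month rule applies only when no investigation there has a month.
2. A recorded progression is never dropped. With no following assessment it stays an event, dated at the scheduled date of that assessment, after the last adequate assessment and no later than the earliest subsequent dated record, including death and the data cut-off. In the traced example the event falls at week 48.

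Where no scheduled date exists (an unscheduled scan, or scanning as clinically indicated after month 36), the text should name the substitute date and keep the same bounds. The midpoint between the last scan and last contact should not be that substitute, because it could place progression long after the scan. Death dates need no change here.

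Apply the rule to any further descriptive PFS analysis under Protocol 10.4.4. Also list any progression assessments dropped for a missing month in the primary analysis; if there are none, report that. The cost is a few sentences, minor programming and one data listing.

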#### **14.2.37 Incomplete dates for last known date patient alive or death**

[figure not shown]
All dates must be completed with day, month and year. If the day is missing, the 15th of the month will be used for incomplete death dates or dates of last contact.

#### **14.2.38 Non-target lesion response**

If no non-target lesions are identified at baseline (and therefore not followed throughout the study), the non-target lesion response at each assessment will be considered 'not applicable (NA)'.

#### **14.2.39 Study/project specific programming**

The standard analysis programs need to be adapted for each study/project.

#### 14.2.40 Censoring reason

In order to summarize the various reasons for censoring, the following categories will be calculated for each time to event variable based on the treatment completion page, the study evaluation completion page and the survival page.

For survival the following censoring reasons are possible:

- Alive
- Lost to follow-up

For PFS and TTP (and therefore duration of responses) the following censoring reasons are possible:

- Ongoing without event
- Lost to follow-up
- Withdrew consent
- Adequate assessment no longer available\*
- Event documented after two or more missing tumor assessments (optional, see [Table 14-7](#))
- Death due to reason other than underlying cancer (*only used for TTP and duration of response*)
- Initiation of new anti-cancer therapy

\*Adequate assessment is defined in [Section 14.2.26](#). This reason is applicable when adequate evaluations are missing for a specified period prior to data cut-off (or prior to any other censoring reason) corresponding to the unavailability of two or more planned tumor assessments prior to the cut-off date. The following clarifications concerning this reason should also be noted:

- This may be when there has been a definite decision to stop evaluation (e.g. reason="Sponsor decision" on study evaluation completion page), when patients are not followed for progression after treatment completion or when only UNK assessments are available just prior to data cut-off).
- The reason "Adequate assessment no longer available" also prevails in situations when another censoring reason (e.g. withdrawal of consent, loss to follow-up or alternative anti-cancer therapy) has occurred more than the specified period following the last adequate assessment.
- This reason will also be used to censor in case of no baseline assessment.

### 14.3 Appendix 3 - Bone Marrow Reserve in Adults

Adapted from R.E. ELLIS: The Distribution of Active Bone Marrow in the Adult, Phy. Med. Biol. 5, 255-258, 1961

#### MARROW DISTRIBUTION OF THE ADULT

SITE		MARROW wt. (g)	FRACTION RED MARROW AGE 40	RED MARROW wt. (g) AGE 40	% TOTAL RED MARROW	
CRANIUM AND MANDIBLE	Head:			136.6		
	Cranium	165.8	0.75	124.3	13.1	13.1
	Mandible	16.4	0.75	12.3		
HUMERI, SCAPULAE, CLAVICLES	Upper Limb Girdle :			86.7	8.3	8.3
	2 Humerus, head & neck	26.5	0.75	20.0		
	2 Scapulae	67.4	0.75	50.5		
	2 Clavicles	21.6	0.75	16.2		
STERNUM AND RIBS	Sternum	39.0	0.6	23.4	2.3	10.2
	Ribs:			82.6		
	1 pair	10.2	All 0.4	4.1	7.9	
	2	12.6		5.0		
	3	16.0		6.4		
	4	18.6		7.4		
	5	23.8		9.5		
	6	23.6		9.4		
	7	25.0		10.0		
	8	24.0		9.6		
	9	21.2		8.5		
	10	16.0		6.4		
	11	11.2		4.5		
12	4.6	1.8				
PELVIC BONES	Sacrum	194.0	0.75	145.6	13.9	36.2
	2 os coxae	310.6	0.75	233.0	22.3	
FEMUR	2 Femoral head and neck	53.0	0.75	40.0		3.8

## 14.4 Appendix 4 - Patient reported outcomes

Figure 14-1 EORTC QLQ-C30

ENGLISH

**EORTC QLQ-C30 (version 3)**

We are interested in some things about you and your health. Please answer all of the questions yourself by circling the number that best applies to you. There are no "right" or "wrong" answers. The information that you provide will remain strictly confidential.

Please fill in your initials:

Your birthdate (Day, Month, Year):

Today's date (Day, Month, Year): 31

---

	Not at All	A Little	Quite a Bit	Very Much
1. Do you have any trouble doing strenuous activities, like carrying a heavy shopping bag or a suitcase?	1	2	3	4
2. Do you have any trouble taking a long walk?	1	2	3	4
3. Do you have any trouble taking a short walk outside of the house?	1	2	3	4
4. Do you need to stay in bed or a chair during the day?	1	2	3	4
5. Do you need help with eating, dressing, washing yourself or using the toilet?	1	2	3	4
During the past week:				
6. Were you limited in doing either your work or other daily activities?	1	2	3	4
7. Were you limited in pursuing your hobbies or other leisure time activities?	1	2	3	4
8. Were you short of breath?	1	2	3	4
9. Have you had pain?	1	2	3	4
10. Did you need to rest?	1	2	3	4
11. Have you had trouble sleeping?	1	2	3	4
12. Have you felt weak?	1	2	3	4
13. Have you lacked appetite?	1	2	3	4
14. Have you felt nauseated?	1	2	3	4
15. Have you vomited?	1	2	3	4
16. Have you been constipated?	1	2	3	4

Please go on to the next page

ENGLISH

**During the past week:**

	Not at All	A Little	Quite a Bit	Very Much
17. Have you had diarrhea?	1	2	3	4
18. Were you tired?	1	2	3	4
19. Did pain interfere with your daily activities?	1	2	3	4
20. Have you had difficulty in concentrating on things, like reading a newspaper or watching television?	1	2	3	4
21. Did you feel tense?	1	2	3	4
22. Did you worry?	1	2	3	4
23. Did you feel irritable?	1	2	3	4
24. Did you feel depressed?	1	2	3	4
25. Have you had difficulty remembering things?	1	2	3	4
26. Has your physical condition or medical treatment interfered with your family life?	1	2	3	4
27. Has your physical condition or medical treatment interfered with your social activities?	1	2	3	4
28. Has your physical condition or medical treatment caused you financial difficulties?	1	2	3	4

**For the following questions please circle the number between 1 and 7 that best applies to you**

29. How would you rate your overall health during the past week?

1      2      3      4      5      6      7

Very poor

Excellent

[figure not shown]
30. How would you rate your overall quality of life during the past week?

1      2      3      4      5      6      7

Very poor

Excellent

**Figure 14-2**    **EQ-5D-5L**

Under each heading, please tick the ONE box that best describes your health TODAY

**MOBILITY**

- I have no problems in walking about
- I have slight problems in walking about
- I have moderate problems in walking about
- I have severe problems in walking about
- I am unable to walk about

**SELF-CARE**

- I have no problems washing or dressing myself
- I have slight problems washing or dressing myself
- I have moderate problems washing or dressing myself
- I have severe problems washing or dressing myself
- I am unable to wash or dress myself

**USUAL ACTIVITIES** (e.g. work, study, housework, family or leisure activities)

- I have no problems doing my usual activities
- I have slight problems doing my usual activities
- I have moderate problems doing my usual activities
- I have severe problems doing my usual activities
- I am unable to do my usual activities

**PAIN / DISCOMFORT**

- I have no pain or discomfort
- I have slight pain or discomfort
- I have moderate pain or discomfort
- I have severe pain or discomfort
- I have extreme pain or discomfort

[figure not shown]
**ANXIETY / DEPRESSION**

- I am not anxious or depressed
- I am slightly anxious or depressed
- I am moderately anxious or depressed
- I am severely anxious or depressed
- I am extremely anxious or depressed

- We would like to know how good or bad your health is TODAY.
- This scale is numbered from 0 to 100.
- 100 means the best health you can imagine.  
0 means the worst health you can imagine.
- Mark an X on the scale to indicate how your health is TODAY.
- Now, please write the number you marked on the scale in the box below.

YOUR HEALTH TODAY =

The best health  
you can imagine

The worst health  
you can imagine

**Figure 14-3 Brief Pain Inventory-Short Form**

STUDY ID# \_\_\_\_\_ HOSPITAL # \_\_\_\_\_

DO NOT WRITE ABOVE THIS LINE

**Brief Pain Inventory (Short Form)**

[figure not shown]
Date: \_\_\_\_/\_\_\_\_/\_\_\_\_ Time: \_\_\_\_\_

Name: \_\_\_\_\_  
Last First Middle Initial

1. Throughout our lives, most of us have had pain from time to time (such as minor headaches, sprains, and toothaches). Have you had pain other than these everyday kinds of pain today?

1. Yes 2. No

2. On the diagram, shade in the areas where you feel pain. Put an X on the area that hurts the most.

3. Please rate your pain by circling the one number that best describes your pain at its **worst** in the last 24 hours.

0 1 2 3 4 5 6 7 8 9 10  
No Pain Pain as bad as you can imagine

4. Please rate your pain by circling the one number that best describes your pain at its **least** in the last 24 hours.

0 1 2 3 4 5 6 7 8 9 10  
No Pain Pain as bad as you can imagine

5. Please rate your pain by circling the one number that best describes your pain on the **average**.

0 1 2 3 4 5 6 7 8 9 10  
No Pain Pain as bad as you can imagine

6. Please rate your pain by circling the one number that tells how much pain you have **right now**.

0 1 2 3 4 5 6 7 8 9 10  
No Pain Pain as bad as you can imagine

**7. What treatments or medications are you receiving for your pain?**

**8. In the last 24 hours, how much relief have pain treatments or medications provided? Please circle the one percentage that most shows how much relief you have received.**

0%	10%	20%	30%	40%	50%	60%	70%	80%	90%	100%
No										Complete
Relief										Relief

**9. Circle the one number that describes how, during the past 24 hours, pain has interfered with your:**

**A. General Activity**

0	1	2	3	4	5	6	7	8	9	10
Does not										Completely
Interfere										Interferes

**B. Mood**

0	1	2	3	4	5	6	7	8	9	10
Does not										Completely
Interfere										Interferes

**C. Walking Ability**

0	1	2	3	4	5	6	7	8	9	10
Does not										Completely
Interfere										Interferes

**D. Normal Work (includes both work outside the home and housework)**

0	1	2	3	4	5	6	7	8	9	10
Does not										Completely
Interfere										Interferes

**E. Relations with other people**

0	1	2	3	4	5	6	7	8	9	10
Does not										Completely
Interfere										Interferes

**F. Sleep**

0	1	2	3	4	5	6	7	8	9	10
Does not										Completely
Interfere										Interferes

**G. Enjoyment of life**

0	1	2	3	4	5	6	7	8	9	10
Does not										Completely
Interfere										Interferes

Copyright 1991 [name]  
Pain Research Group  
All rights reserved.

Appendix 1	CTC grades for laboratory values in Novartis Oncology.....	28

List of tables

Document History – Changes compared to previous version of SAP.....	2
Table 1-1 Study objectives	10
Table 2-1 Last contact date data sources	13
Table 2-1 Patient classification based on protocol deviations and non- protocol deviation criteria	15
Table 3-1 Planned dose intensity.....	19
Table 3-2 Clinically notable ECG values.....	25

List of figures

Figure 1-1 Study Design	9
-------------------------------	---

List of abbreviations

AE	Adverse event
AESI	Adverse events of special interest
ATC	Anatomical Therapeutic Chemical
BOR	Best overall response
CI	Confidence Interval
CBR	Clinical benefit rate
CR	Complete response
CRF	Case Report Form
CRS	Case retrieval sheet
CSR	Clinical study report
CT	Computed tomography
CTCAE	Common Terminology Criteria for Adverse Events
DAR	Dosage administration Record
DI	Dose Intensity
DOR	Duration of Response
ECG	Electrocardiogram
ECOG	Eastern Cooperative Oncology Group
EORTC QLQ-C30	European Organization for Research and Treatment of Cancer Core 30-item Quality of Life Questionnaire
EOT	End of treatment
ER	Estrogen receptor
FAS	Full analysis set
HER2	Human epidermal growth factor receptor 2
HR	Hazard Ratio
HR	Hormone receptor
MBC	Metastatic breast cancer
MedDRA	Medical Dictionary for Regulatory Activities
NCI	National Cancer Institute
NMQ	Novartis MedDRA queries
ORR	Overall response rate
OS	Overall survival
PD	Progressive disease
PDI	Planned dose intensity
PDS	Programming Datasets Specifications
PFS	Progression-free survival
PR	Partial response
PS	Performance Status
PT	Preferred term
QTcF	QT interval corrected by Fridericia method
RDI	Relative dose intensity
RECIST	Response Evaluation Criteria In Solid Tumors

SAE	Serious adverse event
SAP	Statistical Analysis Plan
SD	Stable disease
SD	Standard deviation
SMQ	Standardized MedDRA queries
SOC	System organ class
TFL	Tables Figures and Listings
TBIL	Total Bilirubin

1 Introduction

This document describes the detailed statistical methodology to be used for the final Clinical Study Report (CSR) of study CLEE011F2301, a phase III, randomized, double-blind, placebo-controlled study of ribociclib or placebo in combination with fulvestrant for the treatment of men and postmenopausal women with hormone receptor positive, HER2-negative, advanced breast cancer who have received no or only one line of prior endocrine treatment.

The content of this SAP is based on CLEE011F2301 protocol amendment 4 (Jan 29, 2020). All decisions regarding final analysis, as defined in the SAP document, have been made prior to database lock and unblinding of the study data.

CSR deliverables (shells for tables, figures, listings) and further programming specifications are described in Tables Figures and Listings (TFL) shells and Programming Datasets Specifications (PDS) documents, respectively.

